1.1 Study Design

This is a Phase II multi-center clinical trial with six arms and appropriate stopping rules for poor efficacy.

All subjects in Arm A will receive oral ONC201 every 3 weeks and all subjects in Arm B, C, D, E, and F will receive oral ONC201 every 1 week.

Arm A, B, D, and F will enroll 16-30 evaluable patients each. Arm C will enroll 6 patients who have sufficient resected tumor tissue for correlative studies. Arm E will enroll 12 patients who have sufficient resected tumor tissue for correlative studies. All subjects in Arm C and E will have surgical resection of their tumor 1 day after the second (or more) dose of ONC201.

All subjects will remain on study treatment until progressive disease, unacceptable toxicity, or withdrawal of consent.

All patients will undergo clinical evaluation after each cycle (3 weeks). Neuroimaging studies (contrast-enhanced brain MRI or CT for patients unable to undergo MRI) will be performed at baseline, at 8 weeks from treatment initiation, and then every 8 weeks thereafter.

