8.3.3 Administration

Patients will receive ONC201 while in the clinic for C1D1. Patients can take medications at home for other dosing. The study drug, ONC201, will be supplied in capsule form for oral dosing.

Study patient will receive a 3-week supply of ONC201 during office visit for the first 6 cycles (not applicable to Arm A, which is closed). After the first 6 cycles, the Investigator can prescribe a supply up to 10-weeks beyond the first 6 cycles considering an allowed 10-day window for repeating MRI every 8 weeks.

Patients should take the dose of ONC201 specified by their physician 2 hours prior or 2 hours following food or a meal. If the patient vomits after taking ONC201, they should not retake the dose. Missed doses will not be made up, if more than 3 days from the intended day of administration.

ONC201 should be taken with a glass of water and consumed over as short a time as

possible. Patients should swallow the capsules as a whole and not chew them. Do not crush or empty the capsule. If vomiting occurs during the course of treatment, no re-dosing of the patient is allowed before the next scheduled dose. The occurrence and frequency of any vomiting during a treatment cycle must be noted as an adverse event.

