13. STATISTICAL CONSIDERATIONS

13.1 Study Design

Arm A will accrue at least 16 evaluable patients. Arms B, D, and F will accrue 16-30 evaluable patients each. Arms C will accrue 6 evaluable patients who have sufficient resected tumor tissue for correlative studies. Arm E will accrue 12 evaluable patients who have sufficient resected tumor tissue for correlative studies. Patients in Arm C or E who after surgery are found to have insufficient resected tumor tissue for correlative studies will continue on treatment but will not count towards accrual of that arm. Data on these patients will be collected. In order to accrue 6 patients onto Arm C with sufficient tissue for correlatives following surgical resection, a total of 12 patients could be enrolled onto Arm C. In order to accrue 12 patients onto Arm E with sufficient tissue for correlatives following surgical resection, up to 18 patients could be enrolled onto Arm E.

The study duration is expected to be 7 years: 6 years for accrual, and 1 year for follow-up on the last participant enrolled.

Efficacy analyses will be performed separately for each arm. Patients enrolled in arms other than Arm D with a known H3 K27M mutation in their glioma may be included in the analyses of Arm D. Among recurrent glioblastoma patients, large meta-analyses of clinical trials evaluating a wide array of salvage therapeutics (excluding bevacizumab) have consistently reported PFS-6 rates of 9-11% ([Ballman 2007](#); [Lamborn 2008](#); [Wu 2010](#)). If the true PFS-6 rate on the current study for patients receiving ONC201 were 30% or higher, there would be interest in further investigation of this treatment regimen. Therefore, this study will be used to detect a difference of 20% using a one-

sided binomial test. Statistically, the hypothesis that will be tested is:

H0: $p \leq 0.1$ versus H1: $p > 0.3$

where p is the proportion of patients achieving PFS-6. Enrollment of 30 patients will yield 84% power to detect a 20% difference at an alpha level of 0.05 (one-sided exact test).

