13.2 Interim Analyses

For Arm A, a futility interim analysis will be conducted after 16 patients are enrolled. Since PFS-6 requires at least six months post-study initiation follow-up for subjects without progressive disease, the binary endpoint PFS rate at two months (PFS-2) will be used to determine whether the accrual should be suspended after sixteen patients have accrued. If out of the first 16 patients enrolled, only 7 or less patients are observed to be progression free during the first 2 months after treatment initiation, further accrual in this arm will be discontinued. Assuming exponential distribution, the null and alternative for the PFS6 are translated into 0.44 vs. 0.67 rates for the PFS2. Under these rates the chances of observing 7 or less progression free patients out of the first 16 are 0.6 under the null and 0.046 under the alternative.

For Arm B, D, and F, separately, a futility interim analysis will be conducted after 16 patients who are evaluable for efficacy are enrolled. Since PFS-6 requires at least six months post-study initiation follow-up for subjects without progressive disease, the binary endpoint PFS rate at two months (PFS-2) will be one criteria used to determine whether the accrual should be suspended after sixteen patients have accrued. If out of the first 16 patients who are evaluable for efficacy are enrolled, there is no objective response and only 7 or less patients are observed to be progression free during the first 2 months after treatment initiation, further accrual in this arm will be discontinued. Assuming exponential distribution, the null and alternative for the PFS6 are translated into 0.44 vs. 0.67 rates for the PFS2. Under these rates the chances of observing 7 or less progression free patients out of the first 16 are 0.6 under the null and 0.046 under the alternative.

No interim analyses will be conducted for Arm C or E.

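### Section 13.2 understates the null PFS-2 (0.44; the stated model gives 0.464), so the chance of meeting the PFS-2 futility criterion at a null PFS-6 of 10% is about 0.52, not 0.6

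*Protocol*

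**What the plan says.** Section 13.1 of the protocol tests a PFS-6 of at most 0.1 against 0.3. It supports the null by citing meta-analyses of salvage treatments that "have consistently reported PFS-6 rates of 9-11" percent.

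Section 13.2 places a futility look at 16 patients and uses PFS-2 because PFS-6 would take too long to observe. It names an exponential distribution as the bridge: "the null and alternative for the PFS6 are translated into 0.44 vs. 0.67 rates for the PFS2". It then gives the resulting operating characteristics: the chances of "7 or less progression free patients out of the first 16 are 0.6 under the null and 0.046 under the alternative".

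These sentences appear twice, once for Arm A and once for Arms B, D and F, with the same numbers. The two rules differ. In Arm A the count alone decides. In Arms B, D and F, "further accrual in this arm will be discontinued" only if "there is no objective response and only 7 or less patients are observed to be progression free during the first 2 months". The SAP neither restates nor corrects any of these figures.

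**The concern.** The two conversions should come from one formula, applied once to 10% and once to 30%. The alternative fits that formula and the null does not.

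The null-side probability is what tells a reader how often an arm with an uninteresting PFS-6 would meet the PFS-2 stopping criterion after 16 patients. Section 13.2 is the only place where the documents give it. If it is too high, the futility rule looks better at closing inactive arms than it is. In Arms B, D and F there is a second source of optimism in the same direction: the probabilities cover only one of the two conditions needed to stop, and the text does not say what this means for the chance of stopping.

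**Working it through.** **Inputs.** Null PFS-6 of 0.10 and alternative of 0.30 (section 13.1); cited historical range 9–11% (section 13.1); exponential model, PFS-2 at two months, and a cutoff of 7 or fewer progression-free out of 16 (section 13.2); arm size 16–30 (section 1.1).

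**Step 1: reproduce the plan's binomial figures from its own PFS-2 rates.** With X binomial and n = 16:
- P(X ≤ 7 | 0.44) = 0.595, which rounds to the stated 0.6.
- P(X ≤ 7 | 0.67) = 0.047, against the stated 0.046.

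The binomial step is therefore sound, and any error lies in the rates fed into it.

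**Step 2: convert PFS-6 to PFS-2.** Under an exponential distribution S(t) = exp(−λt), so S(2) = S(6)^(2/6) = S(6)^(1/3).
- Alternative: 0.30^(1/3) = 0.669, which rounds to the stated 0.67.
- Null: 0.10^(1/3) = 0.464, against the stated 0.44.

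**Step 3: look for a reading that rescues 0.44.**
- Working backwards, 0.44³ = 0.085, a PFS-6 of 8.5%. This is below the whole cited range: 9% converts to 0.448 and 11% to 0.479.
- Other time conventions fail. Eight weeks out of 26 gives 0.492 for the null and 0.690 for the alternative; nine weeks out of 26 gives 0.451 and 0.659.
- In general, turning 0.10 into 0.44 needs a time ratio of ln 0.44 / ln 0.10 = 0.357. The same ratio turns 0.30 into 0.651, not 0.67. Conversely, any ratio that gives an alternative rounding to 0.67 puts the null between 0.458 and 0.472.

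No single exponential conversion gives both stated rates from 10% and 30%.

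**Step 4: redo the null probability.**

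| Null PFS-6 | PFS-2 | P(X ≤ 7 of 16) |
|---|---|---|
| 8.5% (implied by 0.44) | 0.44 | 0.595 |
| 9% | 0.448 | 0.569 |
| **10% (section 13.1)** | **0.464** | **0.517** |
| 11% | 0.479 | 0.468 |

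The overstatement at 10% is 0.595 − 0.517 = 0.078. On the alternative side, using 0.669 without rounding to 0.67 gives 0.0475, so that figure is essentially unaffected.

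**Step 5: effect on expected enrolment under the null.** Assume that only the PFS-2 criterion applies and that an arm which is not stopped fills to 30. Then E(N) = 16 + 14 × (1 − P(X ≤ 7)).
- At 0.44: 16 + 14 × 0.405 = 21.7.
- At 0.464: 16 + 14 × 0.483 = 22.8 (22.0 to 23.4 for a null of 9% to 11%).
- Difference: 14 × 0.078 = 1.1 patients per arm.

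If the arm would have closed at 24 instead of 30, the difference is 8 × 0.078 = 0.6; at 20 it is 4 × 0.078 = 0.3.

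**Step 6: Arms B, D and F.** Stopping requires both X ≤ 7 and no objective response. The probability of both cannot exceed the probability of the first. So 0.517 and about 0.047 are upper bounds on the chance of stopping, and 22.8 is a lower bound on expected enrolment for an arm that otherwise fills to 30.

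**The case against.** The strongest counter-argument is that nothing depends on the wrong figures. The rule is a fixed count that never uses 0.44 or 0.6. The error rate that protects an active arm is right, the SAP lists no output that relies on these probabilities, and section 8.3.3 describes Arm A as closed ("not applicable to Arm A, which is closed"). This stands as a limit on the consequences. It does not make the figures right, and they are the protocol's only statement of how often an inactive arm would meet the criterion.

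A second argument is that the null hypothesis covers every PFS-6 up to 10%, so 8.5% lies inside it, and 0.517 is the smallest value the probability takes over that range. This is also true. But 10% is the only null value the protocol names and the one that its 20-point difference is measured from, and 8.5% is stated nowhere. The useful consequence is that the corrected sentence should say that it is evaluated at a PFS-6 of 10%.

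Third, for Arms B, D and F the protocol words its probabilities as the chance of the count, not of stopping, and calls PFS-2 one criterion among those used. Read literally, the sentence is accurate. The extra clause is therefore a clarification and not an arithmetic correction. It is still worth adding, because no other operating characteristics are given for the two-part rule.

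Finally, the enrolment difference of about one patient depends on arms filling to 30. It should be read as a ceiling.

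**Conclusion.** The null-side figures in section 13.2 are wrong under the protocol's own model and hypothesis. At a PFS-6 of 10% the PFS-2 rate is 0.464, not 0.44, and the chance of 7 or fewer progression-free out of 16 is about 0.52, not 0.6 (0.57 to 0.47 across the cited 9–11%). An arm at the null rate would meet the PFS-2 criterion about half the time, 8 percentage points less often than stated. In Arms B, D and F it would stop no more often than that.

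The conclusion rests on the exponential assumption, the two- and six-month time points and the 10% null, all taken from the protocol. The effect is modest: the rule, the cutoff, the arm size and the alternative-side figures stand, and expected enrolment under the null rises by up to about 1.1 patients per arm, with the maximum at 30 patients. For Arm A the correction matters for reporting only.

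**What to change.** In both paragraphs of section 13.2, replace 0.44 with 0.464 and 0.6 with about 0.52, and state that the null figures are evaluated at a PFS-6 of 10%. The alternative-side 0.046 can be tidied to 0.047 when the sentence is reissued. That difference is trivial.

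In the paragraph for Arms B, D and F, add one clause: the probabilities cover the PFS-2 criterion only and, because stopping also requires no objective response, they are upper bounds on the chance of stopping.

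The cost is two numbers in two paragraphs and one clause, with no change to design or conduct. The downside is that the stated chance of stopping an ineffective arm becomes less favourable by about 8 percentage points.

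### The 0.6 and 0.046 printed for the Arm B, D and F futility rule cover only the progression-free count; with the added no-response condition they are upper bounds, and the rule's own stopping probabilities are not given.

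*Protocol*

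**What the plan says.** Protocol section 13.2 sets two futility rules, each applied after 16 patients.

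- **Arm A** has one condition: "If out of the first 16 patients enrolled, only 7 or less patients are observed to be progression free during the first 2 months" from the start of treatment, accrual ends.
- **Arms B, D and F**, each taken separately, have two. PFS-2 "will be one criteria used to determine whether the accrual should be suspended", and accrual ends only if "there is no objective response and only 7 or less patients are observed to be progression free during the first 2 months".

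Both paragraphs then say that, under an exponential distribution, "the null and alternative for the PFS6 are translated into 0.44 vs. 0.67 rates for the PFS2". Both close with the same statement that "the chances of observing 7 or less progression free patients out of the first 16 are 0.6 under the null"; the matching figure for the alternative is 0.046. No other stopping probability is given for Arms B, D and F, and the SAP describes no interim analysis.

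Neither document gives a response rate under the null or the alternative. Section 13.2 does not say which response definition applies. Section 11.1 has two: confirmed CR or PR by RANO-HGG, and confirmed CR, PR or minor response by RANO-LGG. Section 11 says that both criteria are used at each evaluation. Section 13.1 defines ORR as CR or PR by RANO criteria, without naming the version.

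**The concern.** A rule that needs two things to happen cannot trigger more often than one that needs only the first. In Arms B, D and F a single objective response keeps the arm open, however few of the 16 are progression-free. Figures computed from the progression-free count alone therefore do not describe that rule, although they are the only operating characteristics printed after it.

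Section 1.1 promises stopping rules for poor efficacy, and this is the only numerical one for these three arms. Each may accrue 16 to 30 evaluable patients, so the interim governs up to 14 more per arm. An ethics board or investigator would naturally take 0.6 as the chance that an inactive arm is closed at 16. The undefined response condition adds a practical problem: two teams applying different definitions could reach opposite decisions from the same data.

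**Working it through.** **Inputs.** Section 13.2 gives n = 16, a threshold of 7, and PFS-2 of 0.44 (null) and 0.67 (alternative). Section 13.1 gives PFS-6 of 0.10 and 0.30 and a maximum of 30 patients per arm. The response rate r is not given; 0% to 10% is assumed here.

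**Step 1: reproduce the printed figures.** With X ~ Binomial(16, p), P(X ≤ 7) is 0.595 at p = 0.44 (printed 0.6) and 0.0470 at p = 0.67 (printed 0.046, a rounding difference). Both use the progression-free count only.

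**Step 2: add the no-response condition.** Assume that every responder is also progression-free at 2 months. Each patient is then a responder (probability r), progression-free without response (p − r), or progressed (1 − p). The arm stops if there are no responders and at most 7 are progression-free:

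P(stop) = Σ from x = 0 to 7 of C(16, x) · (p − r)^x · (1 − p)^(16 − x)

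**Step 3: check the null PFS-2.** Under the stated exponential assumption, PFS-2 = PFS-6^(1/3). This gives 0.10^(1/3) = 0.464, not 0.44 (0.44³ = 0.085). For the alternative, 0.30^(1/3) = 0.669, which agrees with 0.67.

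**Step 4: expected arm size under the null.** If every continuing arm goes to 30, this is 16 + 14 × (1 − P(stop)). At r = 5% and p = 0.44: 16 + 14 × (1 − 0.302) = 25.8.

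| Assumed r | Null stop, p = 0.44 | Null stop, p = 0.464 | Alternative stop, p = 0.67 | Expected null size, p = 0.44 |
|---|---|---|---|---|
| 0% | 0.595 | 0.517 | 0.0470 | 21.7 |
| 1% | 0.522 | 0.455 | 0.0425 | 22.7 |
| 2% | 0.457 | 0.400 | 0.0385 | 23.6 |
| 5% | 0.302 | 0.267 | 0.0282 | 25.8 |
| 10% | 0.144 | 0.130 | 0.0163 | 28.0 |

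**Step 5: sensitivity to the nesting assumption.** If response were independent of progression status, P(stop) = P(X ≤ 7) × (1 − r)^16. At p = 0.44 this is 0.507, 0.431, 0.262 and 0.110 for r = 1%, 2%, 5% and 10%, somewhat lower than the nested figures.

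**Step 6: effect on the final test.** With 30 patients and no interim, rejecting at 7 or more successes gives one-sided alpha 0.026 and power 0.840, matching the stated 84%. Futility stopping can only remove rejections, so loosening the rule cannot lift type I error above 0.026. The last column but one shows that wrongful stopping of an active arm also falls as r rises.

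**The case against.** The strongest reply is that nothing printed is false. The sentence names its event, 7 or fewer progression-free patients out of 16, and the values are right for that event. The paragraph also says openly that PFS-2 is only one criterion. That stands: this is not a miscalculation. The defect is that the joint probability is missing and a different rule's figures stand in its place.

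A reader might infer that the rule stops an inactive arm far less often than 0.6. The documents do not support that as a fact, because they give no null response rate. The drop is nil at 0%, modest at 1% (0.52) and about half at 5% (0.30), and 10% is a doubtful picture of an inactive arm.

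The rate that counts at the interim may also be below the eventual ORR. Sections 5.3 and 11 put the first scan at 8 weeks and require confirmation at least 4 weeks later. On scheduled imaging, a confirmed response therefore takes about 12 weeks. Under sections 11.3 and 11.5, patients without measurable disease cannot score CR or PR. If confirmed responses are meant, a 2-month look may see few of them. If unconfirmed or minor responses count, there would be more. Section 13.2 leaves this open, which supports asking for the definition but not for choosing one on the sponsor's behalf.

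Finally, the expected sizes assume that continuing arms reach 30. The range is 16 to 30, so 14 further patients per arm is a maximum.

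**Conclusion.** The concern holds in a limited form. For Arms B, D and F, 0.6 and 0.046 are upper bounds on stopping (apart from the rounding of 0.047 to 0.046). The direction is certain and needs no outside figure. The size depends on an unstated response rate: on the protocol's own PFS-2 values, null stopping runs from 0.595 at 0% to 0.14 at 10%, and alternative stopping from 0.047 to 0.016. These values rest on responders being a subset of the progression-free and on r applying to all 16 patients at the time of the look.

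A reader might also infer that the final test is compromised. It is not: the extra condition leaves type I error within that of the 30-patient test and makes wrongful stopping of an active arm less likely. What is overstated is the protection against continued accrual to an inactive arm.

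**What to change.** In the Arm B, D and F paragraph of section 13.2:

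1. Replace 0.6 and 0.046 with the joint probabilities of the two-condition rule over a stated response-rate range that includes 0–1%, or label the two figures as upper bounds that ignore the response condition.
2. Reconcile the null PFS-2 with the exponential assumption before recomputing, so that the new figures are not tied to 0.44 and do not need correcting again.
3. State which response definition the interim condition uses (RANO-HGG or RANO-LGG) and whether confirmation is required by the time of the look.

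This takes a few sentences and changes neither the rule nor the final test. The downside is that the stated futility protection will look less favourable.

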13.3 Statistical Methods for Efficacy Analyses

Efficacy analyses will be performed separately for each arm. Subgroup analyses of the primary tumor location within the brain (e.g. thalamus) and the H3 K27M mutation will be performed across all cohorts. For PFS and OS endpoints, Kaplan-Meier (KM) curves and median estimates from the KM curves will be provided as appropriate. Subjects without efficacy evaluation data or without survival data will be censored at Day 1, as appropriate. Participants without measurable disease will not be included in the analysis of ORR.

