11.1 Definitions

Evaluable for Efficacy and Safety

Patients who have received at least one dose of study drug will be considered evaluable for efficacy and safety. These patients will have response classified according to the definitions stated below.

Evaluable for Intratumoral Concentrations

Patients in Arms C and E must have sufficient tumor tissue from biopsy to permit quantitation of intratumoral concentrations of ONC201 to be considered evaluable for these arms. Patients found to have insufficient tissue may continue treatment, but will be replaced.

Evaluable Non-Target Disease Response

Patients who have lesions present at baseline that are evaluable but do not meet the definitions of measurable disease ($a+b > 10\text{mm}$), have received at least one cycle of therapy, and have had their disease re-evaluated will be considered evaluable for nontarget disease. The response assessment is based on the presence, absence, or unequivocal progression of the lesions.

Disease Parameters

For the purposes of this study, patients should be reevaluated for response at 8 weeks of therapy and then every 8 weeks thereafter. In addition to baseline scan(s), confirmatory scans should also be obtained not less than 4 weeks following initial documentation of objective response.

ORR by RANO-HGG is defined as the proportion of subjects in the analysis population who have confirmed complete response (CR) or partial response (PR) using RANO-HGG criteria. Radiographic assessments will be performed by the investigator for the primary endpoint, but may also be separately assessed by blinded independent central review. Duration of response

is defined as time from first RANO-HGG response (only if confirmed) to disease progression in subjects who achieve a PR or better.

ORR by RANO-LGG is defined as the proportion of subjects in the analysis population who have confirmed CR, PR, or minor response (MR) using RANO-LGG criteria determined by the investigator (but may be separately assessed by blinded independent central review). Duration of response is defined as time from first RANO-LGG response (only if confirmed) to disease progression in subjects who achieve a MR or better.

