11.2 Disease Parameters

Measurable Disease

Bi-dimensionally, contrast-enhancing, measurable lesions with clearly defined margins by CT or MRI scan, with a minimal diameter of 1 cm, and visible on 2 axial slices which are at least 5 mm apart with 0 mm skip. Measurement of tumor around a cyst or surgical cavity, if necessary, requires a minimum thickness of 3 mm. If there are too many measurable lesions to measure at each evaluation, the investigator must choose the largest two to be followed before a participant is entered on study. The remaining lesions will be considered non-measurable for the purpose of objective response determination. Unless progression is observed, objective response can only be determined when all measurable and non-measurable lesions are assessed.

Non-Measurable Evaluable Disease

Unidimensionally measurable lesions, masses with margins not clearly defined, lesions with maximal diameter < 1cm.

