11.3 Response/Progression Categories

The modified RANO Response Criteria to be used in this study are summarized below. If changes in the primary field lesions lead to assessment of progressive disease, this assessment must be confirmed at least 4 weeks later.

11.3.1 Complete response (CR). All of the following criteria must be met:

- a) Complete disappearance of all enhancing measurable and non-measurable disease sustained for at least 4 weeks. In the absence of a confirming scan at least 4 weeks later, this scan will be considered only stable disease.
- b) No new lesions.
- c) All measurable and non-measurable lesions must be assessed using the same techniques as baseline.
- d) Participants must be on no steroids or on physiologic replacement doses only.
- e) Stable or improved non-enhancing (T2/FLAIR) lesions.
- f) Stable or improved clinically, for clinical signs and symptoms present at baseline and recorded to be disease related.

Participants with non-measurable disease cannot have a complete response. The best response possible is stable disease.

11.3.2 Partial response (PR). All of the following criteria must be met:

- a) Greater than or equal to 50% decrease compared to baseline in the sum of products of perpendicular diameters of all measurable enhancing lesions sustained for at least 4 weeks. In the absence of a confirming scan at least 4 weeks later, this scan will be considered only stable disease.
- b) No progression of non-measurable disease.
- c) No new lesions.
- d) All measurable and non-measurable lesions must be assessed using the same techniques as baseline.
- e) The steroid dose at the time of the scan evaluation should be no greater than the dose at time of baseline scan.
- f) Stable or improved non-enhancing (T2/FLAIR) lesions on same or lower dose of corticosteroids compared to baseline scan.
- g) Stable or improved, for clinical signs and symptoms present at baseline and recorded to be disease related clinically.

Participants with non-measurable disease cannot have a partial response. The best response possible is stable disease.

11.3.3 Progressive disease (PD).

Any of the following criterion must be met:

- a) > 25% increase in sum of the products of perpendicular diameters of enhancing lesions (over best response or baseline if no decrease) on stable or increasing doses of corticosteroids.
- b) Any new enhancing measurable lesion.

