The primary efficacy endpoint is PFS-6, defined as the proportion of subjects in the analysis population who remain progression-free for at least six months following initiation of study therapy. Response for the primary analysis will be determined by the investigator assessment, and a confirmation assessment is required per RANO. If patients discontinue protocol therapy at or before 6 months without tumor imaging performed, the patient will be treated in the primary endpoint analysis as a treatment failure. Adjustments will not be made for multiple comparisons.

Secondary efficacy endpoints include: (1) ORR defined as the proportion of subjects in the analysis population who have complete response (CR) or partial response (PR) using RANO criteria; (2) duration of response, defined as time from first RANO response to disease progression in subjects who achieve a PR or better; (3) progression-free survival (PFS), defined as the time from initiation of study therapy to the first documented disease progression according to RANO or death due to any cause, whichever occurs first; and (4) overall survival (OS).

Additional supportive analyses of duration of response and PFS will be conducted using RANO criteria, in which a confirmation assessment of disease progression must be obtained at least 4 weeks after the initial disease assessment indicating progressive disease.

Safety will be assessed by quantifying the toxicities and grades experienced by subjects who have received ONC201, including serious adverse events (SAEs). Other safety endpoints include laboratory safety assessments, KPS status, and vital signs.

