#### 2. General Conventions

The All Treated Analysis Set includes all patients who receive at least one dose of ONC201. This will be used for all analyses.

Unless otherwise specified, continuous variables will be summarized using descriptive statistics [number of observations, mean, standard deviation (SD), median,  $1^{st}(Q1)$  and  $3^{rd}(Q3)$  quartiles, minimum and maximum]. Categorical variables will be summarized as number (percent) of patients.

Day 1 is defined as the date of the first dose of study drug. For events that occur on or after Day 1, study day is defined as (date of event - date of Day 1 + 1). For events that occur prior to Day 1, study day is defined as (date of event - date of Day 1). There is no Day 0. Baseline is defined as the last observed measurement on or before the date of the first dose of study drug.

In general, other than for partial dates, missing data will not be imputed and will be treated as missing. Unless otherwise specified, partial dates will be imputed using the following rules:

- If year is missing, do not impute.
- If only day is missing, impute day as 1st of the month for start dates, end of the month for end dates, and 15th of the month for other dates.
- If day and month are missing, impute as January 1st for start dates, December 31st for end dates, and July 1st for other dates.

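### The SAP's All Treated denominator for ORR departs, without saying so, from the protocol's exclusion of patients without measurable disease, which lowers the CR/PR response rate whenever such patients are treated and anyone responds

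*Protocol*

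**What the plan says.** Protocol Section 13.3 gives a rule specific to ORR: "Participants without measurable disease will not be included in the analysis of ORR". Section 11.3 supplies the reason. Under partial response it says "Participants with non-measurable disease cannot have a partial response. The best response possible is stable disease", and it has a matching sentence for complete response. Section 11.5 likewise limits patients without measurable disease to stable or progressive disease as best response. Section 11.2 defines measurable disease on contrast-enhancing lesions, "with a minimal diameter of 1 cm".

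Other protocol text is broader. Section 11.1 says "Patients who have received at least one dose of study drug will be considered evaluable for efficacy and safety". Section 13.1 lists "ORR defined as the proportion of subjects in the analysis population who have complete response (CR) or partial response (PR) using RANO criteria" and does not repeat the measurable-disease condition.

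The SAP has one population: "The All Treated Analysis Set includes all patients who receive at least one dose of ONC201". It continues: "This will be used for all analyses". SAP Section 3 includes the overall response rate among the planned efficacy analyses, bases it on the investigator's overall RANO response, and assigns it to Table 2.3. Nothing there restricts the denominator or mentions Protocol 13.3.

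**The concern.** A programmer who follows the SAP will divide by all treated patients. A reader of the protocol will expect division by those with measurable disease. If any treated patient lacks measurable disease, the two rates differ whenever there is a response, and Table 2.3 would give no sign of which one it shows.

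Such patients can be enrolled. The eligibility criteria do not require measurable disease: recurrence documented on biopsy is enough, and Arm E does not need recurrent disease. Section 11.1 has an evaluability category for patients whose baseline lesions "do not meet the definitions of measurable disease", so the protocol expects some.

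ORR is a listed secondary objective. At stake is whether the published rate estimates the quantity the protocol describes.

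**Working it through.** The documents give no ORR target, no ORR sample size and no count of patients without measurable disease, so there is no stated ORR figure to reproduce. The check is algebra on the documents' rules, followed by an illustration.

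**Inputs**
- N: treated patients (the SAP Section 2 denominator).
- k: treated patients without measurable disease at baseline. Not given; assumed 0 to 30% of N.
- r: patients with confirmed CR or PR. Not given; assumed. By Sections 11.3 and 11.5 none of the k patients can be among the r.

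**Formulas**
- Protocol ORR (13.3) = r / (N - k)
- SAP ORR = r / N
- SAP ORR / protocol ORR = (N - k) / N = 1 - k/N

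For CR/PR the SAP rate can therefore never exceed the protocol rate. The two are equal if k = 0 or r = 0. Otherwise the SAP rate is lower, by the relative amount k/N.

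**Illustration, N = 30 (upper end of the planned size for Arms B, D and F), r = 5**

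| k | SAP ORR | Protocol ORR | Difference (points) |
|---|---|---|---|
| 0 | 5/30 = 16.7% | 5/30 = 16.7% | 0 |
| 3 | 16.7% | 5/27 = 18.5% | 1.9 |
| 6 | 16.7% | 5/24 = 20.8% | 4.2 |
| 9 | 16.7% | 5/21 = 23.8% | 7.1 |

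Differences are taken before rounding. At the lower end, N = 16 with r = 3, the SAP rate is 3/16 = 18.8%. The protocol rate is 3/14 = 21.4%, 3/13 = 23.1% or 3/11 = 27.3% for k = 2, 3 or 5.

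**Scale against sampling error.** With r = 6 and N = 30 the All Treated rate is 20.0%, exact 95% interval 7.7% to 38.6%. With k = 6 the protocol rate is 6/24 = 25.0%, interval 9.8% to 46.7%. The shift is small beside the interval, but it goes one way and can be avoided.

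**Does the direction hold for RANO-LGG?** Not necessarily. Section 11.1 counts minor response towards RANO-LGG ORR, and Section 11.3.4 defines minor response on T2/FLAIR lesions only, whereas measurable disease in Section 11.2 is contrast-enhancing. Sections 11.3.1 and 11.3.2 rule out CR and PR for non-measurable disease but do not mention minor response; the stable-or-progressive limit in Section 11.5 would exclude it. Suppose N = 30, k = 6, six responders with measurable enhancing disease, and two minor responders without it who are counted despite Section 11.5. The All Treated rate is then (6 + 2)/30 = 26.7%, above 6/24 = 25.0%.

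**The case against.** The best defence is that the SAP agrees with part of the protocol. Section 11.1 makes every dosed patient evaluable for efficacy, and Section 13.1 defines ORR over an analysis population without qualification. That stands as a real inconsistency within the protocol, and the fix should remove it. It does not rescue the SAP: the sentence in 13.3 is explicit and specific to ORR, while the others are general.

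The SAP also calls itself abbreviated and refers to an ISE SAP where approaches are the same. That document was not available and may hold a measurable-disease rule. But the ONC006 SAP states its own set for all analyses and does not invoke such a rule for ORR. If one exists, the two need reconciling.

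A further objection is that the effect may be nil and is at most modest. This is fair: it is zero if k or r is zero, and the illustrative values of k are assumptions.

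A reader might infer more than the documents support:
- That the SAP's ORR is too low in all circumstances. The RANO-LGG example shows the direction can reverse, and the SAP's reference to overall RANO response does not say which criteria apply.
- That comparisons between arms are distorted. Protocol 13.3 analyses each arm separately and neither document plans a between-arm ORR comparison. The SAP tabulates by arm, so k/N may differ across columns, but no planned inference rests on that.
- That Sections 11.1 and 11.2 give contradictory size thresholds, so that a 6 x 6 mm lesion is measurable under one and not the other. This needs a+b in Section 11.1 to mean the sum of two diameters, and the protocol defines neither letter. The expression is unclear; a contradiction is not shown.

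**Conclusion.** The mismatch is real. Followed as written, the SAP yields a CR/PR (RANO-HGG) ORR equal to the protocol's ORR times (1 - k/N), strictly lower once at least one treated patient lacks measurable disease and at least one patient responds. Assumed shares of 10%, 20% and 30% without measurable disease lower the rate by those same relative amounts. The true size cannot be stated because the documents do not report k.

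The conclusion rests on 13.3 governing the ORR denominator and on the Section 11.3 and 11.5 limits being applied. It does not extend to RANO-LGG ORR, where the protocol has no matching definition of measurable T2/FLAIR disease. PFS-6 is unaffected, and the interim condition of no objective response does not depend on this denominator. This should be settled before Table 2.3 is produced, but it is a secondary-endpoint matter.

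**What to change.** 1. In SAP Section 3 and the Table 2.3 note, compute RANO-HGG ORR in treated patients with measurable enhancing disease at baseline per Protocol Section 11.2. Show the All Treated rate beneath it as a labelled sensitivity row, and report k by arm. If the sponsor prefers All Treated as the main denominator, the SAP should say so and justify the departure from 13.3.
2. For RANO-LGG ORR, base the denominator on measurable T2/FLAIR disease and define it. Applying Section 11.2 here would drop non-enhancing patients whose T2/FLAIR lesions those criteria are meant to assess. Reconcile the best-response limit in Section 11.5 with the minor-response rules in Sections 11.1 and 11.3.4, and state in the SAP which criteria each reported ORR uses.
3. Clarify a+b > 10mm in Section 11.1 so that it agrees with Section 11.2, and align the evaluable-for-efficacy wording in 11.1 with 13.3.

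The cost is wording in both documents and a few rows in one table. The main ORR will rest on somewhat fewer patients, so its interval will be a little wider: for 6 responders with k = 6, 36.9 points (46.7 - 9.8) instead of 30.9 (38.6 - 7.7).
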